4.8.2 AE date imputation

The following missing dates will not be imputed

- Missing AE start dates
- AE start dates missing the year
- Partial/missing AE end dates

AE with uncertain relationship will be considered as treatment-emergent AE.

For other types of missing dates, the rules specified in [Tables 4-7](#) to [Table 4-10](#) will be used.

Table 4-7 AE/treatment date abbreviations

	Day	Month	Year
Partial Adverse Event Start Date	<not used>	AEM	AEY
Treatment Start Date (TRTSTD)	<not used>	TRTM	TRTY

[Table 4-8](#) describes the possible combinations and their associated imputations. The upper text indicates the imputation (NC, A, B, C etc.) and the lower text the relationship of the AE start date to the treatment start date (TRTSTD).

Table 4-8 Imputation algorithm

	AEM MISSING	AEM < TRTM	AEM = TRTM	AEM > TRTM
AEY MISSING	NC	NC	NC	NC
	Uncertain	Uncertain	Uncertain	Uncertain
AEY < TRTY	(D)	(C)	(C)	(C)
	Before TRTSTD	Before TRTSTD	Before TRTSTD	Before TRTSTD
AEY = TRTY	(B)	(C)	(B)	(A)
	Uncertain	Before TRTSTD	Uncertain	After TRTSTD
AEY > TRTY	(E)	(A)	(A)	(A)
	After TRTSTD	After TRTSTD	After TRTSTD	After TRTSTD

The legend to the above table is shown in [Table 4-9](#).

Table 4-9 Imputation algorithm legend

Relationship		
Before TRTSTD		Indicates AE start date prior to Treatment Start Date
After TRTSTD		Indicates AE start date after Treatment Start Date
Uncertain		Insufficient to determine the relationship of AE start date to Treatment Start Date
Imputation calculation		
NC / Blank		No convention/imputation
(A)		01MONYYYY
(B)		TRTSTD+1
(C)		15MONYYYY

Relationship

(D)	01JULYYYY
(E)	01JANYYYY

A few examples are shown in [Table 4-10](#).

Table 4-10 Example scenarios

Partial AE start date	Treatment start date	Relationship with TRTSTD	Imputation Calculation	Imputed Date
12MMYY	20OCT2001	Uncertain	NC	<blank>
DDMM2000	20OCT2001	Before	(D)	01JUL2000
DDMM2002	20OCT2001	After	(E)	01JAN2002
DDMM2001	20OCT2001	Uncertain	(B)	21OCT2001
DDSEP2001	20OCT2001	Before	(C)	15SEP2001
DDOCT2001	20OCT2001	Uncertain	(B)	21OCT2001
DDNOV2001	20OCT2001	After	(A)	01NOV2001

4.8.3 Concomitant medication date imputation

The imputation of the start date of concomitant medication will follow the same conventions as for AE dates. Partial concomitant medication end dates will not be imputed.

4.8.3.1 Prior therapies date imputation

Start date

The same rule which is applied to the imputation of AE/concomitant medication start date will be used with the exception that for scenario (B) it will be replaced with “start date of study drug -1”.

End date

- Imputed date = min (reference end date , last day of the month), if day is missing
- Imputed date = min (reference end date , 31DEC), if month and day are missing

Reference end date will be the start date of study drug.

If the end date is not missing and the imputed start date is after the end date, use the end date as the imputed start date. If both the start date and the end date are imputed and if the imputed start date is after the imputed end date, use the imputed end date as the imputation for the start date.

Incomplete date of progression –Prior antineoplastic therapy-medication

A missing day is defaulted to the 1st of the month. However, date of progression should be expected to be after start date of prior antineoplastic therapy.

- Imputed date = max (start date of prior antineoplastic therapy, 1st day of the month), if day is missing

4.8.3.2 Post therapies date imputation

Start date

- Imputed date = max (reference start date, first day of the month), if day is missing
- Imputed date = max (reference start date , 01JAN), if day and month are missing

Reference start date will be the last date of study treatment administration + 1.

End date

No imputation.

4.8.4 Other imputations

Incomplete date of initial diagnosis of cancer and date of most recent recurrence

A missing day is defaulted to the 15th of the month and a missing month and day is defaulted to 01JAN.

If because of this imputation the chronology of the events is altered then the imputation should be made to the minimum value up to where chronology remains unchanged. E.g. if due to imputation the date of most recent recurrence becomes prior to the initial diagnosis date then it should be set to initial diagnosis date.

Incomplete assessment dates for tumor assessment

All investigation dates (e.g. MRI scan, CT scan) must be completed with day, month and year. If one or more assessment dates are incomplete but other investigation dates are available, the incomplete date(s) are not considered for calculation of the assessment date and assessment date is calculated as the latest of all investigation dates (e.g. MRI scan, CT-scan) if the overall lesion response at that assessment is CR/PR/SD/UNK. Otherwise – if overall response is progression – the assessment date is calculated as the earliest date of all investigation dates at that evaluation number. If all measurement dates have no day recorded, the 1st of the month is used. If the month is not completed, for any of the investigations, the respective assessment will be considered to be at the date which is exactly between the previous and the following assessment. If a previous and following assessment is not available, this assessment will not be used for any calculation.

[figure not shown]
Incomplete or missing death date

For cases when either day is missing or both month and day are missing for the date of death, the following imputation rules will be implemented:

- If only day is missing, then impute 15th day of the month and year of death.
- If both day and month are missing, then impute 01JUL of the year of death.

Exposure-adjusted overall incidence

- Start date of study treatment will be considered as the AE start date for any AE with missing start date for exposure-adjusted overall incidence calculation.

5 Reference:

Brookmeyer R and Crowley J (1982). A Confidence Interval for the Median Survival Time, *Biometrics* 38, 29 - 41.

Clopper CJ, Pearson ES (1934). The use of confidence or fiducial limits illustrated in the case of the binomial. *Biometrika*; 26, 404-413.

Collet D (1994). Modelling survival data in medical research. London, Chapman & Hall.

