2.3 Patient demographics and other baseline characteristics

The FAS will be used for all patient demographic and baseline characteristic summaries and listings.

Basic demographic and background data

All demographic and baseline disease characteristics data will be summarized and listed by cohort. Categorical data (e.g. gender, race, ethnicity, ECOG performance status) will be summarized by frequency count and percentages. Continuous data (e.g. age, weight, height, BMI) will be summarized by descriptive statistics (as defined in [Section 2.1](#)).

Diagnosis and extent of cancer

Descriptive statistics and frequency counts and percentages will be tabulated by cohort, as appropriate, for diagnosis and extent of cancer based on the data collected on the electronic Case Report Form (eCRF) including: primary site of cancer, tumor histology/cytology, histological grade, time (in months) since initial diagnosis of primary site, stage at initial diagnosis, time (in months) from initial diagnosis to first recurrence/progression, time (in months) since most recent relapse/progression, current extent of disease (metastatic sites), number of metastatic sites at baseline, types of lesions (target and non-target lesions) at baseline, number of target lesions at baseline, and disease burden at baseline for target lesion (based on the data collected on the RECIST eCRF page).

Medical history

Medical history and ongoing conditions, including cancer-related conditions and symptoms will be summarized and listed by cohort. Separate summaries will be presented for ongoing and historical medical conditions. The summaries will be presented by primary system organ class and preferred term. Medical history and current medical conditions are coded using the Medical Dictionary for Regulatory Activities (MedDRA) terminology.

Prior anti-cancer therapy

Prior anti-neoplastic (anti-cancer) therapy will be listed in three separate categories by cohort: 1. medications, 2. radiotherapy, and 3. surgery.

The number and percentage of patients who received any prior anti-neoplastic medications, prior anti-neoplastic radiotherapy or prior anti-neoplastic surgery will be summarized by cohort.

Prior anti-neoplastic medications will be summarized by chemotherapy (medication) setting, other therapy (medication) setting, number of prior regimens of anticancer medications and

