If a patient has not progressed or is not known to have died at the date of analysis cut-off, PFS will be censored at the date of the last adequate tumor evaluation before the cut-off date. PFS events documented after the initiation of new anti-neoplastic therapy (i.e. RECIST 1.1 documented disease progression or death) will be considered for the primary analysis provided tumor assessments continue after initiation of the new cancer therapy. Clinical deterioration will not be considered as a qualifying event for progression. Refer to [Table 2-1](#) for censoring and event date options and outcomes for PFS.

In particular, PFS will be censored at the last adequate tumor assessment if one of the following occurs: absence of event; the event occurred after two or more missing tumor assessments (see [Section 4.6.1](#)). See also [Section 4.6.1](#) describing the special case of a missing baseline tumor assessment.

Patients with no BIRC data will be considered censored at the start date of study drug.

PFS will be described in tabular and graphical format using Kaplan-Meier methods as described for DOR by cohort, including estimated median (in months) with 95% CI, 25th and 75th percentiles and Kaplan-Meier estimated probabilities with corresponding 95% CIs at several

time points. Censoring reasons will also be summarized by cohort. These analyses will be performed separately based on BIRC assessment and based on investigator assessment.

In addition, PFS table will be repeated on the PPS.

Overall survival (OS)

OS is defined as the time from the start date of study drug to the date of death due to any cause. If the patient is alive at the date of the analysis cut-off or lost to follow-up, then OS will be censored at the last contact date prior to data cutoff date (see [Section 4.3](#) for further details on derivation of last contact date).

OS will be described in tabular and graphical format using Kaplan-Meier methods as described for DOR by cohort, including estimated median (in months) with 95% CI, 25th and 75th percentiles and Kaplan-Meier estimated probabilities with corresponding 95% CIs at several time points. Censoring reasons will also be summarized by cohort.

OS from initial diagnosis to the date of death due to any cause will also be analyzed. Date of censoring is the same as defined for OS analysis.

Duration of Follow-up

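### Year-only dates of initial diagnosis and most recent recurrence are set to 1 January, so time since diagnosis, time since last relapse and OS from diagnosis can only be lengthened or left unchanged

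*SAP*

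**What the plan says.** SAP 4.8.4 (Other imputations) gives one rule for incomplete dates of initial diagnosis and most recent recurrence: "A missing day is defaulted to the 15th of the month and a missing month and day is defaulted to 01JAN". If the imputed date disturbs the order of events, "then the imputation should be made to the minimum value up to where chronology remains unchanged". The SAP's example is a recurrence that falls before diagnosis and is reset to the diagnosis date.

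The same section treats incomplete death dates differently. With the day missing: "If only day is missing, then impute 15th day of the month and year of death". With day and month missing: "If both day and month are missing, then impute 01JUL of the year of death".

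The diagnosis and recurrence dates feed these outputs:

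- SAP 2.3, baseline tables: "time (in months) since initial diagnosis of primary site" and "time (in months) since most recent relapse/progression", and also the interval from diagnosis to first recurrence or progression.
- SAP 2.8.1: "OS from initial diagnosis to the date of death due to any cause will also be analyzed". For that analysis, "Date of censoring is the same as defined for OS analysis".

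The SAP gives no reason for choosing 1 January.

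**The concern.** One sentence of SAP 4.8.4 applies two different principles. When only the day is missing, the date is placed near the middle of what is possible. When day and month are missing, it is placed at the lower limit. 1 January cannot be later than the true date, so the error has one sign for any interval that starts at the imputed date and ends at a date fixed independently of it.

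For OS from diagnosis, the end date (death or censoring) is the same as in the main OS analysis, so an earlier origin adds survival time day for day. The added days lie before the true diagnosis, and every patient in the FAS lived at least to first dose. The added time therefore carries no risk of death and no information.

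At stake are the disease-history table and one supplementary survival output.

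**Working it through.** **No plan figure to reproduce.** The documents give no expected duration and no count of incomplete dates. The check is calendar arithmetic, and the uniform distributions used below are assumptions.

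**Definition.** Error = true date minus imputed date, in days. This equals imputed interval minus true interval when the interval starts at the imputed date. A month is 30.4375 days (SAP 4.4).

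**1. Year-only, whole year possible.** True day d uniform on 1 to 365.
- 1 January (day 1): mean of (d − 1) = (0 + 364)/2 = 182 days; 182/30.4375 = 5.98 months; range 0 to 364. Leap year: mean 182.5, range 0 to 365.
- 1 July (day 182): mean 183 − 182 = +1 day, range −181 to +183.

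**2. Day missing, 15th of the month.** Over all days of a 365-day year, the mean error is +0.7 days, range −14 to +16. The day-missing rule is about centred; the year-only rule is not.

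**3. A later event in the same year.** If the true date is uniform from 1 January to a cap on day C, the mean error is (C − 1)/2 under 1 January. Under 1 July, moved back to the cap where needed, it is (C + 1)/2 − min(182, C).

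| Cap | C | 1 January | 1 July, capped |
|---|---|---|---|
| 31 March | 90 | +44.5 | −44.5 |
| 30 June | 181 | +90 | −90 |
| 30 September | 273 | +136 | −45 |
| 31 December | 365 | +182 | +1 |

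The 1 January error shrinks but keeps its sign. Plain 1 July changes the sign and understates.

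**4. The chronology clause.** Take, for illustration, a known diagnosis on day 100 and a recurrence dated only to the same year, uniform on days 100 to 365 (mean (100 + 365)/2 = 232.5). Uncorrected, 1 January gives 232.5 − 1 = 231.5 days. The clause moves the recurrence to day 100, which leaves 232.5 − 100 = 132.5 days. The error is reduced but still has one sign, because the date moves only to the earliest value allowed.

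**5. Diagnosis to first recurrence.** Both ends can be imputed, so there is no fixed direction:
- diagnosis year-only, recurrence known: lengthened or unchanged;
- diagnosis known, recurrence year-only: shortened or unchanged, and zero days apart if the clause resets recurrence to diagnosis;
- both year-only in different years: the errors largely offset.

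The imputation rule also names the most recent recurrence, whereas this table variable uses the first.

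**6. Cohort level.** Shift in the group mean = share affected × 5.98 months. Assumed shares of 1%, 5%, 10% and 20% give 0.06, 0.30, 0.60 and 1.20 months. In the combined treatment-naive MET-mutant group (N = 60, SAP 2.2), one such date adds 5.98/60 = 0.10 months to mean time since diagnosis.

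**7. Midpoint between bounds.** For a date uniform between a lower bound L and an upper bound U, the midpoint (L + U)/2 equals the mean, so the mean error is 0 apart from rounding. With no other event in the year, (1 + 365)/2 = day 183, or 2 July.

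**The case against.** The best defence is that the choice is partly conventional and the outputs are minor. The SAP's date rules are mixed. It also uses 1 January for adverse events with onset in a year after the treatment-start year (Tables 4-8 and 4-9) and for year-only starts of post-treatment therapy (4.8.3.2). It uses the first of the month for progression on prior therapy (4.8.3.1) and for tumor assessments with no day recorded (4.8.4). So 1 January does not breach a uniform SAP convention. That stands, and the point rests instead on the direction of the error and the contrast within 4.8.4. A further contrast is that year-only prior-therapy starts go to 1 July when the year precedes the treatment-start year (4.8.3.1, through rule D of the adverse-event tables). A patient whose diagnosis and prior-therapy start are both dated only to the same earlier year is therefore given a gap of 182 − 1 = 181 days by the rules alone.

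The limits on impact also stand. The number of year-only dates could be zero. OS is summarised by Kaplan-Meier medians and percentiles, which may move less than a mean. OS from diagnosis does not appear among the secondary efficacy analyses in protocol 10.5.2, and no hypothesis uses it.

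A reader might go further in three ways that the documents do not support:

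- That every disease-history interval is inflated. Time from diagnosis to first recurrence can move either way.
- That the distortion is worst in treatment-naive patients because they are dosed soon after diagnosis. Neither document says so, and inclusion criterion 4 admits patients to Cohorts 5 and 7 who relapsed more than 12 months after (neo)adjuvant therapy, so their initial diagnosis may be old.
- That the chronology clause has no effect. It does reduce the error for some recurrence dates.

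**Conclusion.** The point holds as a minor one. For each patient with a year-only date, SAP 4.8.4 can only overstate, or leave unchanged, time since initial diagnosis, time since most recent relapse and OS from initial diagnosis. The mean overstatement is about 182 days (range 0 to 364) if the true date is uniform over the year, and less if a later event falls in that year or the chronology clause acts on a recurrence date.

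The sign follows from the rule itself; the size rests on the uniform assumption. The cohort-level effect cannot be stated, because the share of year-only dates is not given. A reader might infer that the trial's efficacy results are flattered. They are not: ORR, DOR, PFS and OS from first dose do not use these dates. Nor do the documents show that the population would look materially more indolent.

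**What to change.** In SAP 4.8.4, replace the 1 January default for year-only dates of initial diagnosis and most recent recurrence with the midpoint between:

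- the later of 1 January and any known earlier event (for recurrence, the diagnosis date); and
- the earlier of 31 December and the earliest known later event (start of prior therapy, relapse or first dose, as applicable).

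This gives about 1 July when no other event falls in that year, and it keeps the order of events. It also avoids the understatement that a plain 1 July rule would bring when a later event falls in the same year. The 15th-of-month rule for a missing day can stay.

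Add a footnote to the OS-from-diagnosis and disease-history tables giving the number of imputed dates. That is worth doing even if 1 January is kept, because it shows whether the matter has any practical effect.

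The cost is one SAP line and one extra derivation, with no new data. Reported intervals may become slightly shorter and could differ a little from those in the reports listed in SAP 2.1, if those used the 1 January rule.

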#### **14.1.34 Calculation of 'time to event' variables**

Time to event = end date - start date + 1 (in days)

When no post-baseline tumor assessments are available, the date of randomization/start of treatment will be used as end date (duration = 1 day) when time is to be censored at last tumor assessment, i.e. time to event variables can never be negative.

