#### **14.1.36 Incomplete dates for last known date patient alive or death**

All dates must be completed with day, month and year. If the day is missing, the 15th of the month will be used for incomplete death dates or dates of last contact.

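### Partial death dates are imputed with no known-alive floor, and partial AE start dates with no check against a complete AE end date, so some imputed dates can be impossible

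*SAP*

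**What the plan says.** **Death dates.** SAP 4.8.4 gives two rules. Day missing: "If only day is missing, then impute 15th day of the month and year of death". Day and month missing: "If both day and month are missing, then impute 01JUL of the year of death". Neither refers to another date. Protocol 14.1.36 has the same day-missing rule (the 15th "of the month will be used for incomplete death dates or dates of last contact"), also without a check, and does not cover the year-only case. SAP 4.3 allows partial-date imputation for deaths, but it derives a last contact date only for patients not known to have died, so that date sets no lower limit for a death. The imputed date feeds OS directly (SAP 2.8.1: "OS is defined as the time from the start date of study drug to the date of death due to any cause"), and death is also an event in PFS and DOR.

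**AE start dates.** Table 4-8 in SAP 4.8.2 compares the partial start with the month and year of treatment start. A start in the same month, or in the same year with the month missing, is labelled *Uncertain* and set to the day after treatment start. The section adds: "AE with uncertain relationship will be considered as treatment-emergent AE". A complete AE end date plays no part. SAP 4.8.3 applies the same conventions to concomitant medication start dates.

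**Elsewhere in the SAP.** SAP 4.8.3.1 reuses the AE start rule for prior therapies with one change, and adds a guard for when a complete end date exists and "the imputed start date is after the end date, use the end date as the imputed start date". Dose end dates (4.8.1), post-treatment therapy starts (4.8.3.2) and diagnosis or recurrence dates (4.8.4, under their own heading) also have chronology guards.

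**The concern.** An imputation rule should not contradict dates already in the database. The death rule can record a patient as dead while dosing, visits or scans show the patient alive, and it can return a negative survival time. The AE rule can give an event an onset after its own recorded end and move a pre-treatment event into the on-treatment tables.

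The outputs exposed are OS, PFS and DOR where the event is a death, the on-treatment death tables, AE incidence, and the time-to-onset and duration analyses for AEs of special interest. Other date types in the same part of the SAP are guarded, so this looks like an omission.

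**Working it through.** **Inputs.** The rules are those of SAP 4.8.4 and Tables 4-8 and 4-9. The time-to-event formula is end date minus start date plus 1 day (Protocol 14.1.34). Every patient date below is assumed, except the treatment start of 20OCT2001, which comes from Table 4-10.

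**1. The plan's own examples.** Tables 4-8 and 4-9, coded as written, reproduce all seven rows of Table 4-10, including the October 2001 start with day missing, which becomes 21OCT2001.

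**2. Deaths.** The last column floors the death at the last complete known-alive date.

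| First dose | Last contact | Death as recorded | Rule date | OS as written (days) | OS with floor (days) |
|---|---|---|---|---|---|
| 15SEP2018 | not specified | 2018 | 01JUL2018 | -76 + 1 = -75 | at least 1 |
| 20OCT2017 | 05DEC2017 | 2017 | 01JUL2017 | -111 + 1 = -110 | 46 + 1 = 47 |
| 20OCT2017 | 27OCT2017 | OCT2017 | 15OCT2017 | -5 + 1 = -4 | 7 + 1 = 8 |
| 01MAR2017 | 20NOV2017 | 2017 | 01JUL2017 | 122 + 1 = 123 | 264 + 1 = 265 |
| 01MAR2017 | 28NOV2017 | NOV2017 | 15NOV2017 | 259 + 1 = 260 | 272 + 1 = 273 |

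A last contact on 10NOV2021 with a death recorded as 2021 puts the death 132 days before the patient was last known alive. The largest backdating is 183 days for a year-only date (31DEC against 01JUL) and 31 - 15 = 16 days when only the day is missing. In a 365-day year, 183 dates fall after 01JUL and 185 after the 15th of their month, so no unusual calendar is needed.

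**3. Event status.** SAP 4.6.1 treats an event more than D2 = 2 × 6 + 2 = 14 weeks (98 days) after the last adequate scan as following two missing assessments, and PFS is then censored. Take a last scan on 01AUG2021 without progression and a true death on 20DEC2021. The gap is 141 days, so PFS is censored at 01AUG2021. If only the year is recorded, the death moves to 01JUL2021. It then counts as a PFS event dated before that scan, provided an earlier adequate scan lies within 98 days.

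**4. AEs.** First dose 20OCT2001, AE start October 2001 with day missing, AE end 05OCT2001. The imputed start is 21OCT2001, 16 days after the event ended, and the AE is treatment-emergent. For an AE of special interest, time to first occurrence is 21 - 20 + 1 = 2 days. For a first grade 3/4 event, duration is 5 - 21 + 1 = -15 days. With the start capped at the end date, onset is 05OCT2001 and the event is pre-treatment.

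**The case against.** Several counter-arguments have force.

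- **Data quality.** Protocol 14.1.36 asks for complete dates, survival contact is every 3 months (Protocol 4.1.5), and missing values are queried (Protocol 9.4). This makes partial deaths less common. It does not exclude them, and SAP 4.3 and 4.8.4 expect them.
- **Ordinary approximation.** If no later contact is recorded, the 15th or 01JUL is a reasonable convention. A reader might infer that every imputed death is wrong; only those that conflict with a known date are.
- **AE timing is checked.** A reader might infer that the AE rule ignores chronology altogether. It does not: Table 4-8 compares month and year with treatment start, and an earlier known month is placed before treatment. Only the check against a complete end date is absent.
- **The AE error is narrow and conservative.** AEs are captured from main consent (Protocol 8.1.1) and screening normally spans 28 days, so few events can qualify, and the error adds events to the safety tables without hiding any. Treating truly uncertain events as emergent is a sound convention. It has no justification where the end date already settles the matter.
- **Protocol conflict.** Protocol 14.1.34 says "time to event variables can never be negative", and a reader might infer that the SAP breaches this. That sentence explains the 1-day convention for censoring at the last tumor assessment when no post-baseline assessment exists. It is not a rule on imputed deaths.
- **Stakes.** ORR does not depend on these dates, and OS, PFS and DOR are descriptive Kaplan-Meier summaries.

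**Conclusion.** The point holds as a defect in the written rules. Followed literally, SAP 4.8.4 can place a death up to 183 days (year only) or 16 days (day missing) before the patient was last known alive, and can return negative survival times. SAP 4.8.2 can count as treatment-emergent an AE already known to have ended before first dose, and SAP 4.8.3 carries the gap to concomitant medications.

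The size per affected patient follows from the calendar. The number affected does not: the documents give no count of partial dates. That it is small is an assumption, and no shift in a median or an AE rate can be estimated. The hypothesis tests on ORR are untouched. The change is worth making because the resulting values are impossible, the SAP already guards comparable dates, and the repair is cheap.

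**What to change.** **Deaths (SAP 4.8.4).** Impute the later of the rule date and the patient's last complete known-alive date, never before first dose, and cap it at the end of the recorded month or year and at the data cut-off. Define the known-alive date for deceased patients from dated contacts such as dosing, visits, assessments and samples. Table 4-2 cannot be borrowed unchanged: it serves patients not known to have died, and it admits end-of-treatment dates without condition and AE end dates. Adding a day to the known-alive date is best avoided, since a contact on 30NOV with a death recorded in November would give 01DEC. Query any known-alive date later than the recorded month or year.

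**AEs and concomitant medications (SAP 4.8.2, 4.8.3).** If a complete end date precedes the imputed start, set the start to the end date, as 4.8.3.1 already does. Classify an AE whose complete end date is before first dose as pre-treatment. Keep the treatment-emergent convention for AEs that remain uncertain.

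**Cost.** A few SAP sentences and a few lines of code, with no new data collection.
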